## 15.8 Overview of Plans for Manuscript #4: Long-term Benefits / Harms

The primary analyses for manuscript #4 will rely on a linear model for change from baseline(T1) to one year post treatment (T5) for each PRO variable conditional on baseline covariates which include *cirrhosis status, age, race, sex at birth, treatment regimen, cirrhosis-by-regimen* interaction, and the *baseline PRO score*. Including the baseline PRO score as a covariate has several advantages for clarity of interpretation and improved precision of estimators of interest. The analysis will focus on point estimates and confidence intervals. As an aid to interpretation of the primary results, and for purposes of generating new hypotheses, auxiliary longitudinal analyses of the repeated measures will also be explored. The PRO variables of interest in manuscript #4 are described here by aim:

Aim 4a, MSAS. The outcome variable will be change from baseline (T1 to T5) in the total MSAS score. As an aid to interpretation, additional supportive tabulations for each of the 32 side effects will be examined; e.g., change in side effects/pre-existing symptoms will be characterized in regard to the raw frequency, severity and distress items.

Aim 4b, PROMIS. The primary analyses will focus on 10 symptom-specific PROMIS® T-scores and 1 HIT headache score. The outcome variable will be change from baseline (T1 to T5) in the total score. As an aid to interpretation of the main results, additional supportive tabulations for specific survey items will be examined.

Aim 4c, Pre-existing medical conditions. For each of several patient selected pre-existing conditions at baseline, we will descriptively examine which conditions stay the same, get worse, or get better one year after treatment ends. For the primary analyses, the outcome variable will be change from baseline (T1 to T5).

Aim 4d, HCV-PRO. The outcome variable will be change from baseline (T1 to T5).

Aim 4e, Cirrhosis differences. For each regimen we will evaluate the apparent effect of cirrhosis status on change from baseline (T1 to T5) for each of the outcome variables (4a, 4b, 4c, 4d). The results will be obtained from the models fitted for Aims 4a, 4b, 4c and 4d.

Auxiliary analyses comparing treatment regimens. Although not the purpose of this study, we will also take the opportunity to examine similarities and differences between regimens. Causal inference methods (section 15.10) will be used to fit response models similar to those fitted for Aims 3a, 3b, 3c and 3d.

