## 3 STUDY AIMS

### 3.1 Specific Aims

This study is focused on characterizing several HCV treatment regimens in terms of HCV-associated symptoms, treatment side effects, medication adherence, out of pocket costs, and long-term benefits of cure and harms associated with all-oral treatments for chronic hepatitis C, as indicated by the following patient-reported outcomes (PROs) collected before, during and up to one year after HCV treatment:

Aim 1: Evaluate changes from baseline (T1) to during treatment (T2, T3) to characterize harms associated with each treatment regimen (*see manuscript #1 below*) in terms of the following measures:

- 1a. The Memorial Symptom Assessment Scale (MSAS)
- 1b. Specific side effects as measured by multiple PROMIS surveys

- 1c. HCV-specific functional status as measured by the HCV-PRO
- 1d. Pre-existing medical conditions
- 1e. Cumulative out of pocket costs during treatment

Aim 2: Evaluate differences in medication adherence between patients with and without history of mental health/substance abuse (MH/SA Hx) (see *manuscript #2 below*)

- 2a. Characterize and compare the two groups (with and without MH/SA Hx) on medication adherence while accounting for treatment regimen and pill burden.
- 2b. Estimate the effects of pill burden on medication adherence in the combined sample.
- 2c. Estimate the prevalence rates of reasons for nonadherence in the combined sample.
- 2d. Estimate the effect of medication adherence on the SVR rate at 3 months post-treatment.

Aim 3: Evaluate changes from baseline (T1) to 3 months after end of treatment (T4) to characterize short-term benefits of cure in the combined sample of patients (see *manuscript #3 below*)

- 3a: Amelioration of HCV-associated symptoms as measured by the MSAS and PROMIS surveys
- 3b. HCV-functional status as measured by the HCV-PRO

Aim 4: Evaluate changes from baseline (T1) to 1 Year (T5) after end of treatment to characterize long-term benefits or harms (see *manuscript #4 below*)

- 4a. Long-term symptoms as measured with the MSAS
- 4b. Long-term side effects as measured by PROMIS surveys
- 4c. Pre-existing medical conditions
- 4d. HCV-functional status, as measured by the HCV-PRO
- 4e. Differences in 4a-4d between patients with and without cirrhosis

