### 3.2 Auxiliary Aims

The main objective of this study is to characterize a number of benefits and harms associated with DAA treatment and viral cure as described in Aims 1-4. However, we will also take the opportunity to examine similarities and differences between the treatment regimens using causal inference methods (see *manuscripts #1 and #3 below*.)

Planned Manuscripts to Address Specific Aims 1-4		Analysis
Aim 1: Treatment Side Effects	Manuscript describing PRO changes from baseline to during treatment to characterize each regimen in terms of treatment harms such as side effects (T2/T3 data). Auxiliary analyses will compare regimens.	page 22,25-26
Aim 2: Medication Adherence	Manuscript on medication adherence will compare patients with and without history of mental health/substance abuse, characterize the effects of adherence on SVR rate, explore reasons for nonadherence, and evaluate effects of pill burden on adherence.	page 22,25-26
Aim 3: Benefits of achieving SVR	Manuscript evaluating changes from baseline to 3-months post-treatment (T4) in HCV symptoms and other PROs in patients who achieve SVR to characterize short-term benefits of cure. The main analysis will characterize change in PROs for the total sample and auxiliary analyses will explore differences between regimens.	page 23,25-26
Aim 4: Long-term Benefits/Harms	Report of long-term patient reported harms and benefits associated with HCV treatment at 1 year post-treatment. Evaluate changes in PROs from baseline to T5, and evaluate differences between patients with and without cirrhosis. Auxiliary analyses will explore differences between regimens.	page 23,25-26
PRO Psychometrics	Manuscript to evaluate the psychometric properties of several PROs (HCV-PRO, MSAS, PROMIS) in the HCV population	
Study Protocol	Manuscript describing the PROP UP study design, methodology, and protocol	
Baseline Characteristics	Manuscript describing baseline patient characteristics of the study sample, including HCV-associated symptoms, pre-existing medical conditions, and functional status.	

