#### **15.3 Supportive longitudinal analysis and interpretation of changes from baseline**

HCV-related symptom scores will be measured longitudinally. As an aid to interpretation of the primary results, and for purposes of generating new hypotheses, auxiliary longitudinal analyses of these repeated measures may also be explored.

Any increments from Baseline (T1) during treatment (T2/T3) will represent worsening of HCV-related symptoms or commencement of new onset treatment side effects. Similarly, decrements from Treatment (T2/T3) to 12-weeks post-treatment (T4) will represent amelioration or disappearance of symptoms. For any

symptoms remaining at T4, decrements from T4 to T5 will represent further healing. Thus for each individual the longitudinal trajectories of the scores represents that individual's history of waxing and/or waning of HCV-related symptoms. Secondarily, complementary analyses of each of the 32 symptoms will be used to investigate whether side effects that begin during treatment tend to resolve and to investigate the incidence of new symptoms or side effects that appear after treatment ends.

Treatment-related side-effects scores will also be measured longitudinally. Ideally, any increment from T1 to T2/T3 will be completely reversed by a decrement from T2/T3 to T4 or T5. Thus for each individual, the longitudinal trajectories of the scores represents that individual's history of waxing and/or waning treatment-related side-effects and HCV-related symptoms. These trajectories will be summarized descriptively via estimates of occasion-specific mean levels (with confidence intervals) and in terms of patterns of the trajectories represented, for example, by the proportion of patients for whom all treatment-related side-effects disappeared by T4/T5.

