#### **15.5 Overview of Plans for Manuscript #1: Change in Treatment Side Effects from T1 to T2/T3**

The primary analyses for manuscript #1 will rely on a linear model for change from baseline for each PRO variable conditional on baseline covariates which include *cirrhosis status, age, race, sex at birth, treatment regimen, cirrhosis-by-regimen interaction*, and the *baseline PRO score*. Inclusion of the baseline PRO score as a covariate has several advantages for clarity of interpretation and improved precision of estimators of interest. The analysis will focus on point estimates and confidence intervals.

PRO variables of interest in manuscript #1 are described here by aim:

Aim 1a, MSAS. The outcome variable will be change from baseline (T1) to the larger of the two MSAS scores (T2 and T3) during treatment. As an aid to interpretation, additional supportive tabulations for each of the 32 side effects will be examined; e.g., the incidence of new side effects and the exacerbation of existing symptoms during treatment will be characterized in regard to the raw frequency, severity and distress items.

Aim 1b, PROMIS®. The primary analyses will focus on 6 side effect-specific PROMIS® T-scores and 1 HIT headache score. The outcome variable will be change from baseline (T1) to the larger of the two T-scores (T2 and T3) during treatment. As an aid to interpretation of the main results, additional supportive tabulations for specific survey items will be examined.

Aim 1c, HCV-PRO. In the primary analysis, the outcome variable will be change from baseline to the larger of the two HCV-PRO scores (T2 and T3) during treatment.

Aim 1d, Pre-existing medical conditions. For each of several selected pre-existing condition at baseline, we will descriptively examine which conditions stay the same, get worse, or get better, during HCV treatment.

Aim 1e, OOP Costs. This outcome variable will be patient-reported cumulative (T2-T4) direct costs and indirect costs on  $\log_{10}$  scale. Sensitivity analyses will include use of a generalized log-linear model. Treatment differences in OOP costs could affect adherence and / or persistence and hence impact SVR. The co-variation of OOP costs with other outcomes will be explored in order to generate new hypotheses about the role of OOP costs.

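### Aims 1d and 4c follow only medical conditions already present at T1, so a condition that first appears during treatment or by T5 is not counted

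*Combined protocol and SAP*

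**What the plan says.** Section 3.1 sets up Aim 4 "to characterize long-term benefits or harms", and the manuscript table in Section 3.2 describes its product as "Report of long-term patient reported harms and benefits associated with HCV treatment at 1 year post-treatment". Medical conditions are one component (Aim 4c), with a counterpart during treatment (Aim 1d).

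For Aim 4c, Section 15.8 says: "For each of several patient selected pre-existing conditions at baseline, we will descriptively examine which conditions stay the same, get worse, or get better", judged one year after treatment ends. The next sentence adds: "For the primary analyses, the outcome variable will be change from baseline (T1 to T5". For Aim 1d, Section 15.5 again starts from selected conditions at baseline: "we will descriptively examine which conditions stay the same, get worse, or get better, during HCV treatment". Aim 4e then carries the Aim 4c outcome into the cirrhosis comparison: "For each regimen we will evaluate the apparent effect of cirrhosis status on change from baseline".

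The instrument appears in Table 3 (Section 8.1) only as a checklist, with no item count. Table 4 (Section 11.4) schedules the conditions form at T1, T2, T3 and T5.

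For symptoms the plan goes further. Aim 1a says that "the incidence of new side effects and the exacerbation of existing symptoms during treatment will be characterized", and Section 15.3 plans analyses of the 32 MSAS symptoms "to investigate the incidence of new symptoms or side effects that appear after treatment ends".

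**The concern.** A report on harms and benefits should be able to show a change in either direction. The three categories in Aims 1d and 4c describe the course of a condition the patient already has. A patient who did not have it at T1 and has it at T3 or T5 has changed in the direction of harm, yet nothing in the stated rule tabulates that change.

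If the rule is followed as written, a reader of manuscript #1 or #4 learns whether existing conditions improved or deteriorated but not how many new ones were reported. The same blind spot passes into Aim 4e: patients with and without cirrhosis could have the same better/same/worse split and different numbers of new conditions, and the comparison would not show it.

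**Working it through.** No figure in the plan is at issue, so the check is mainly of text.

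**Step 1: list the possible transitions for one condition from T1 to follow-up.**

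| At T1 | At follow-up | Category in Aims 1d and 4c |
|---|---|---|
| Present | Present, worse | Worse |
| Present | Present, unchanged | Same |
| Present | Present but milder, or gone | Better |
| Absent | Absent | Outside the stated set |
| Absent | Present | Outside the stated set |

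The last row is the gap. The third row also matters: improvement need not mean resolution, so the plan's tally is not a present/absent count.

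**Step 2: look for the missing row elsewhere in the plan.**
- Section 15.3 and Aim 1a count new events, but only MSAS symptoms and side effects.
- PROMIS, HIT and HCV-PRO enter as score changes. They do not count conditions.
- Table 5 (Section 13), the chart extraction 12 weeks after treatment, records treatment dates and duration, viral load, SVR and laboratory values. It does not record new diagnoses.
- Table 4 repeats the mental health and the alcohol and drug items at T5, but no onset analysis is defined for them.
- Section 19.3 makes harms unrelated to study participation non-reportable to the coordinating university, so adverse events do not fill the gap.

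No section defines an outcome for new-onset conditions.

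**Step 3: what the added table could show.** The onset rates, T1 prevalence and loss used here are assumptions; the documents give none of them. The number at risk is N × (1 − T1 prevalence). With the planned N = 1600, 20% prevalence and no loss, that is 1600 × 0.80 = 1280. Wilson 95% intervals:
- 1% onset: 13 cases, 0.6% to 1.7%.
- 2% onset: 26 cases, 1.4% to 3.0%.
- 5% onset: 64 cases, 3.9% to 6.3%.

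Overall rates would therefore be estimated usefully. Single regimens are another matter. Take the Appendix's planned numbers per cirrhosis group and assume 25% loss and 25% T1 prevalence:
- Harvoni: 480 × 0.75 × 0.75 = 270 at risk.
- Viekira Pak: 40 × 0.75 × 0.75 = 22.5 at risk. With no onsets among 22, the exact two-sided 95% upper limit is 1 − 0.025^(1/22) = 15.4%.

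In the small regimen cells, counts are all that can sensibly be given.

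**The case against.** **The follow-up form is not shown.** Wording about staying the same, worsening or improving fits a form that asks only how each ticked condition has changed. If so, there are no unreported onset data and the gap is one of collection. This stands: the form has to be checked before the remedy is costed.

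**The text may already include onset.** Aim 4c names change from baseline as its outcome, Aim 4e draws on models fitted for Aim 4c, and Section 15.2 plans logistic models for binary outcomes on all 1600 participants. A model that included baseline-negative patients would contain absent-to-present change. But the subject of those sentences is conditions pre-existing at baseline, and no onset outcome is defined. If onset was intended, one sentence would settle it.

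**It is a matter of scope.** Both sub-aims are titled as concerning pre-existing conditions, and what happens to those is a fair question. New symptoms that patients feel are covered by the MSAS, and Section 15.1 leaves room for descriptive and exploratory work. That limits the importance of the point but does not remove it: optional exploration does not commit the authors to reporting new conditions in aims meant to describe harms.

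**Two stronger readings are not supported.** A reader might infer that the tally leans toward benefit by a calculable amount. It does not follow: the plan has a category for worsening, improvement is not the same as resolution, and no prevalence or onset rates are given. A reader might also infer that a clear cirrhosis difference in onset would be hidden. Pooling regimens, an assumed 15/450 versus 30/450 gives a 95% interval (Newcombe) of 0.5 to 6.3 points. But Aim 4e is specified by regimen. In Harvoni, the largest, the same assumed rates give 9/270 versus 18/270, a difference of 3.3 points with an interval of −0.4 to 7.3, which includes zero.

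**Conclusion.** The point holds in a limited, descriptive form. As written, Aims 1d and 4c cover only conditions present at T1, and no other analysis counts a medical condition that first appears during treatment or by T5. Worsening of existing conditions, new MSAS symptoms and change in the score-based PROs are all captured. No error rate, power figure or sample size is affected.

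The size of the omission cannot be derived from the documents, and neither a direction nor an amount of bias should be claimed. The conclusion rests on reading the baseline restriction in both aims at face value. Whether the gap lies in analysis alone or also in data capture depends on the follow-up form. This is a cheap improvement worth making, not a flaw that threatens the study's main results.

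**What to change.** Keep the better/same/worse table in Aims 1d and 4c and label it as among patients with the condition at T1. Beside it, for each checklist condition, give the number and rate of new reports with a 95% CI among patients without it at T1: by T2/T3 for Aim 1d and by T5 for Aim 4c, with actual denominators. Show both tables by cirrhosis status, with counts only in small regimen cells. Label the results descriptive and not attributable to treatment, since there is no untreated group.

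First confirm that the full checklist is asked at T2, T3 and T5, and whether it asks about current conditions or any past diagnosis. Report net prevalence change only in the former case; under an ever-diagnosed question prevalence can only rise.

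The cost is SAP wording and one extra table in each of manuscripts #1 and #4. If the follow-up form re-asks only conditions ticked at T1, a small form change is needed as well, and it cannot recover data from participants already assessed. Sample size and visits are unchanged.

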## 15.9 No Interim Analysis

Interim analyses will be conducted for two purposes: (1) To coincide with submission of abstracts to professional conferences and (2) To use portions of the earlier data as it accrues for protocol monitoring, and development and coding of statistical algorithms in SAS. Blinding to treatment condition or group will be used if deemed necessary. Interim analyses for the purpose of early treatment or study discontinuation, as a function of evidence of treatment efficacy, safety issues, or futility, will not be conducted.

## 15.10 Role of Causal Inference Methods

The participants will comprise two or more regimen-specific treatment cohorts. The auxiliary analyses comparing regimens will require application of causal inference methods.

Two stages of analysis. The causal inference analysis strategy comprises **(1) a design stage** involving estimation and use of a propensity score model for purposes of achieving balance of baseline covariates, and **(2) an outcomes analysis stage** for treatment effect estimation and inference separately for each outcome variable. For these two stages we may rely on the approach proposed by Cao et al. building on previous work by Tan, Robins et al, Funk et al and others. Rotnitzky et al proposed a competing approach and compared the performance of their method to that of Cao et al.. In the manner of Cao et al., we will use an improved doubly robust (DR) estimator obtained via enhancements in the estimation of the propensity score model and the inverse-probability weighted (IPW) outcome model. Confidence intervals will rely on bootstrap methods. Similar analytic methods will be employed to compare patient subgroups or different treatment durations.

Sensitivity Analyses and Diagnostics. Both stages will involve careful use of diagnostic methods (e.g., for covariate balance) and an extensive set of sensitivity analyses. Additionally, to ensure covariate balance in each of the two cirrhosis subgroups, it will be necessary to take steps in the design stage to, for example, appropriately account for subgroup differences in the propensity score model and examine subgroup-specific diagnostics for covariate balance and for propensity score distribution overlap.

Unverifiable Assumptions. All baseline variables that have a causal effect on treatment assignment and on the outcome variables must be included in the set of covariates used in the design stage. The required assumption of “no unmeasured confounders” is unverifiable. Although limited by the necessity of making additional assumptions and conjectures, efforts will be made to investigate the potential magnitude of residual bias that would exist if any unmeasured confounders exist. Additionally, if a strong instrumental variable (IV) has been identified for use in analysis of a particular outcome variable, then an auxiliary analysis will be performed using the IV approach however, the IV results would only be used to guide confidence in the main results obtained by the IPW approach and would not replace those results. The unverifiable assumption of the IV approach is that the instrument is not correlated with an unobservable error term.

### 15.11 Methods for Coping with Missing Data

The analysis plan relies on an extensive set of covariates measured at baseline. For purposes of estimation of the propensity score model, missing covariate values will be addressed via multiple imputation; furthermore, for each participant, the resulting multiplicity of propensity scores will be averaged together as proposed by Mitra and Reiter. The alternatives (e.g., average results from multiple outcome models) will be explored for purposes of sensitivity analysis. More generally, best practices for dealing appropriately with incomplete data, especially PROs, will depend on the documented causes of the missing, censored, or coarsened values. Every effort will be made to document the causes and to avoid incomplete data by capturing the PRO data even when the participant terminates treatment earlier than scheduled. Depending on the mechanisms which cause loss-to-follow-up for outcomes such as the MSAS at 1 year, multiple imputation methods may be appropriate.

Competing model-based methods will be examined for purposes of sensitivity analysis.

### 15.12 Overview of Sample Size Considerations

The proposed PROP UP sample size is N = 1600 participants. The rationale for this choice was based on aim-specific considerations of the availability of eligible subjects, feasible rates of recruitment, the length of time available to conduct the study, the per-subject costs in time and effort, and considerations of the anticipated levels of precision of estimators and the anticipated levels of power of statistical hypothesis tests. The 1600 participants will comprise two to five treatment cohorts. Participants receiving Harvoni® are expected to comprise about 60% of the participants (n ≈ 960), while perhaps 5% will receive Viekira Pak® (n ≈ 80) and 10% may receive Zepatier® (n ≈ 160). Other treatment cohorts may comprise 10% (n ≈ 160), or 15% (n ≈ 240) shares of the total sample size of 1600 participants. These numbers are approximations based on the current treatment landscape, and are subject to change. In each treatment cohort, subgroups of interest are expected to be about equally prevalent; for example, about 50% will have cirrhosis, and for example about 50% are expected to have a history of mental health conditions or substance abuse. In contrast, the subgroup of participants who achieve SVR is anticipated to comprise roughly 94% of the total sample size (n ≈ 1500).

